### **12.2.2 Suicidal ideation**

Suicidal ideation-related events will be reported to the IRB as indicated by the DAIDS Table for Grading the Severity of Adult and Pediatric Adverse Events, Version 2.0. [November 2014] described above. In addition, participants will be offered support and access to mental health services available at the study site. Study staff will ensure study participants are linked to care.

## **13 DISCONTINUATION AND REPLACEMENT OF PARTICIPANTS**

### **13.1 Early Discontinuation of Study Drug**

A participant may be discontinued from study treatment at any time if the participant, or the investigator, feels that it is not in the participant's best interest to continue. The following is a non-exclusive list of possible reasons for study treatment discontinuation:

- Participant withdrawal of consent
- Participant is not adhering with study procedures
- Adverse event that in the opinion of the investigator would be in the best interest of the participant to discontinue study treatment
- Protocol violation requiring discontinuation of study treatment; including change or interruption of the HT regimen
- Lost to follow-up
- Sponsor request for early termination of study
- Positive pregnancy test (performed outside of the study settings)

If a participant is withdrawn from treatment due to an adverse event, the participant will be referred to care.

All participants who discontinue study treatment will be withdrawn from the study and every effort will be made to welcome participant for an early withdrawal visit as soon as possible at which the procedures listed in section 10.5 should be performed. At this visit, reasons for stopping the study will be documented, if participant is willing to share.

All participants are free to withdraw from participation at any time, for any reason, specified or unspecified, and without prejudice.

Reasonable attempts will be made by the investigator to provide a reason for participant withdrawals. The reason for the participant's withdrawal from the study will be specified in the participant's source documents Refer to Section 10.5 for early termination procedures.

### **12.3 Withdrawal of Participants from the Study**

A participant may be withdrawn from the study at any time if the participant, or the investigator feels that it is not in the participant's best interest to continue.

All participants are free to withdraw from participation at any time, for any reason, specified or unspecified, and without prejudice.

Reasonable attempts will be made by the investigator to provide a reason for participant withdrawals. The reason for the participant's withdrawal from the study will be specified in the participant's source documents. As noted above, participants who discontinue study treatment early (i.e., they withdraw prior to week 4) should have an early withdrawal visit. Refer to Section 10.5 for early termination procedures. Participants who withdraw after week 0 but prior to week 1 should be encouraged to come in for a withdrawal visit.

### **12.4 Replacement of Participants**

Participants who withdraw from the study treatment may be replaced.

## **14 PROTOCOL VIOLATIONS**

A protocol violation occurs when the participant, or investigator fails to adhere to significant protocol requirements affecting the inclusion, exclusion, participant safety and primary endpoint criteria. Protocol violations for this study include, but are not limited to, the following:

- Failure to meet inclusion/exclusion criteria
- Use of a prohibited concomitant medication
- Failure to adhere to study drug regimen
- Failure to participate in the daily directly observed therapy (2 or more failed calls with no back up documentation of pill taking)
- Change or interruption of HT regimen

- Failure to comply with Good Clinical Practice (GCP) guidelines will also result in a protocol violation. The Sponsor, in this case the principal investigators, will determine if a protocol violation will result in withdrawal of a participant.

When a protocol violation occurs, it will be discussed with the investigator and a Protocol Violation Form detailing the violation will be generated and submitted to the IRB. A copy of the form will be filed in the site's regulatory binder.

## **15 STATISTICAL METHODS AND CONSIDERATIONS**

Prior to the analysis of the final study data, a detailed Statistical Analysis Plan (SAP) will be written describing all analyses that will be performed. The SAP will contain any modifications to the analysis plan described below.

### **15.1 Data Sets Analyzed**

All eligible and dosed participants who are enrolled into the study and receive all doses of the study drug will be included in the pharmacokinetic analysis.

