### 9.4.3 Administration Instructions

Participants who enroll in the study will schedule a face to face video calls plan with the study clinician. Calls will occur daily at a time that is convenient for the participant. Calls will last 60 seconds in duration and will be focused on watching the FTC/TDF tablet be placed into the mouth, swallowed, and the mouth opened to verify the table is no longer present. Before the table is ingested, the participant will be asked a question about food ingestion in the prior hour or intent to eat in the next hour.

Participant are encouraged not to take the study drug outside of the video call setting. However, if participant cannot perform a video call for the DOT (no Wi-Fi, cell phone dies...), the pill taking can happen over an audio phone call, or back up documentation of the pill taking such as filming oneself taking the pill may be done. The time stamped video will be shared with study team at the next visit. In last resort, if none of these options are possible, a simple text such as "Hi *study clinician's name*, dosing at hh.mm on dd-mmm, Thanks" could be sent to the team. If the daily DOT call is not documented, it will be considered a missed dose.

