#### **9.6 Measures of Treatment Adherence**

Daily adherence will be directly observed by participants taking part in real time DOT video calls, or witnessed by study staff at the study visit if the drug is taken at the clinic. Study staff will monitor the FTC/TDF tablet be placed into the mouth, swallowed, and the mouth opened to verify the table is no longer present. Alternate documentations of pill taking as described in 9.4.1 may be used as back up measures if access to video capacity is impossible for participant. DOT will be recorded daily by the study team to document on the Drug Dispensation, Hormones and DOT log. Repeated failure to adhere to the DOT regimen will lead to discontinuation from study participation.

If participant fails to connect with study staff for the call, study staff will make every possible attempt to connect with participant. If participant misses the call and does not provide back up evidence of pill taking, it will be considered a missed dose.

If participant misses two or more study drug doses, the participant will be excluded from study participation.

DOT calls will capture hormone therapy adherence as well, which may be either directly observed if feasible, or verbal self-report. Hormone adherence will be captured on the Drug Dispensation, Hormones and DOT log.

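### The PK set is defined by person (all doses received), so a single undocumented dose can discard weekly samples drawn while the participant was fully dosed

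*Combined protocol and SAP*

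**What the plan says.** Section 15.1 is the only definition of the PK analysis set. It covers eligible, dosed, enrolled participants who "receive all doses of the study drug will be included in the pharmacokinetic analysis". It has no rule for individual samples.

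What counts as a miss is set in section 9.4.3: "If the daily DOT call is not documented, it will be considered a missed dose". Section 9.6 adds that there must be no back-up evidence of pill taking.

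Retention is governed elsewhere:
- Section 9.6: "If participant misses two or more study drug doses, the participant will be excluded from study participation", and "Repeated failure to adhere to the DOT regimen will lead to discontinuation from study participation".
- Section 14: the item on observed dosing starts at "2 or more failed calls with no back up documentation of pill taking". The same list also has "Failure to adhere to study drug regimen", with no number attached, and the principal investigators "will determine if a protocol violation will result in withdrawal of a participant".
- Section 13.1: "Participant is not adhering with study procedures" is a possible, not a mandatory, reason for stopping treatment.

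Dried blood spots are drawn at weeks 0 to 4 (section 10.3.1). Section 15.3 fits a linear mixed model to log TFV-DP at weeks 1 to 4, with unstructured covariance and a group comparison at each week. Section 15.4 states power for 48 participants (24 per group) and does not mention how many will be evaluable.

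**The concern.** Set side by side, these rules give three outcomes. With no missed dose, the participant is followed and analysed. With two or more, the participant is excluded from participation. With exactly one, the participant may be followed to week 4 but does not meet section 15.1.

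The miss need not be a pill that was not taken: a documentation failure on one day is enough. If it falls in the last week, three weekly samples drawn while fully dosed go with it. The mixed model accepts incomplete series, so nothing in the analysis method requires this. The same loss applies to samples drawn before the first miss in participants later excluded under section 9.6.

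What is at stake is the number of valid observations in the primary comparison, and so its precision.

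**Working it through.** **Inputs from the documents.** Two-sided 0.05; 0.52 log with 48 participants gives 81% power (all trans participants against MSM controls); 0.70 log with 24 gives 80% (one group against MSM controls), all from section 15.4. 28 daily doses (section 9.4.1). Samples at weeks 1 to 4.

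**Not in the documents, so assumed.** The per-dose miss rate p; misses independent across days; the SD of log TFV-DP; the number of MSM controls.

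**Step 1: reproduce the stated power.** The fold changes fit natural logs: exp(0.52) = 1.68 and exp(0.70) = 2.01. Solving both power statements together with a two-sample noncentral t gives SD 1.174 and 295 controls:
- Pooled: 0.52 / [1.174 × √(1/48 + 1/295)] = 2.85, power 81.0%.
- One group: 0.70 / [1.174 × √(1/24 + 1/295)] = 2.81, power 80.0%.

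The control number is sensitive to rounding in the stated figures, so a range is shown in step 3.

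**Step 2: who is dropped.** Take 48 completers with at most one miss, those with two or more having been replaced, and one-miss completers not replaced.
- P0 = (1−p)^28; P1 = 28p(1−p)^27; q = P1/(P0+P1).
- Dropped = 48q; PK n = 48(1−q).
- If the miss is equally likely on any day, the expected number of weekly samples drawn before it is 0.75 + 0.50 + 0.25 + 0 = 1.5 of 4. Fully dosed samples lost = 1.5 × 48q.

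Example, p = 0.5%: P0 = 0.869, P1 = 0.122, q = 0.123; dropped 5.9; PK n 42.1; samples lost 8.9. Then 0.52 / [1.174 × √(1/42.1 + 1/295)] = 2.69, power 76.4%.

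| p | Dropped of 48 | Fully dosed samples lost | Pooled power | One-group power |
|---|---|---|---|---|
| 0.1% | 1.3 | 2.0 | 80.1% | 79.0% |
| 0.25% | 3.1 | 4.7 | 78.7% | 77.5% |
| 0.5% | 5.9 | 8.9 | 76.4% | 75.0% |
| 1% | 10.6 | 15.9 | 72.1% | 70.3% |

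**Step 3: sensitivity to the back-solved values.** With 160 controls (SD 1.108) to 880 controls (SD 1.235), the SD re-solved each time to give 81% at n = 48, pooled power is about 80%, 79%, 76–77% and 71–73% at the four rates.

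**Step 4: what a sample-level rule gives back.** If samples before the first miss are kept, n at week w is 48(1 − qw/4). Treating each week as a separate comparison:
- p = 0.5%: n = 46.5, 45.0, 43.6, 42.1; power 79.9%, 78.8%, 77.7%, 76.4%.
- p = 1%: n = 45.4, 42.7, 40.1, 37.4; power 79.1%, 77.0%, 74.6%, 72.1%.

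The week 4 sample count does not rise. Under the mixed model, however, earlier visits of the same participants also inform week 4. Summing the inverse correlation matrices over the observed-visit patterns, inverting, and taking the reciprocal of the week 4 diagonal gives an effective n (covariance treated as known). At p = 1% and assumed visit correlation 0.5 to 0.9 (compound symmetric or first-order autoregressive), this is about 38 to 44 instead of 37.4, and power about 73% to 78% instead of 72%. The separate-week figures therefore understate the gain at weeks 2 to 4.

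Pre-miss samples from participants excluded under section 9.6 add about 0.02, 0.09, 0.35 and 1.3 at the four rates. They are not counted in these powers.

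**Step 5: is there bias?** Let a missed dose on day j lower the level at day d by the factor 1 − r^(d−j)(1−r)/(1−r^d), with r = 2^(−1/T) and half-life T assumed to be 5 to 30 days. Averaged over random miss days and multiplied by q, keeping post-miss samples would shift mean log TFV-DP by at most about 0.009 at p = 1% and 0.014 at p = 2%, against a target of 0.52.

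**The case against.** **Different rules for different purposes.** Sections 9.6 and 14 decide who stays in the study; section 15.1 decides who enters the PK analysis. A reader might infer that the sections contradict each other. They do not: a stricter analysis set is coherent, and section 6.1 says the PK analyses depend on adherence. This stands. What remains is that the rule works by person where the data and the model work by visit, so it discards samples that satisfy its own fully dosed intent.

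**The exclusion is inferred.** Section 15.1 says who will be included and never says only. Withdrawal after one miss is possible under sections 13.1 and 14, and section 15 promises a later SAP that may modify the plan. All of this is right, and it is why the point says may and natural reading. But if 15.1 leaves nobody out it defines no set, and no modifying text is in the documents.

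**Replacement.** Section 9.4.4 allows replacement of those who fail the observed-dosing regimen, with no threshold, so it can reach a one-miss participant. Used that way it would restore most of the power. It is optional, and it would not bring back the discarded samples.

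**The miss rate may be very low.** Video, audio call, self-recording and text must all fail. At 0.1% to 0.25% the pooled loss is only about 1 to 2 points, and no passage supports the higher rates. This stands.

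**Why not simply keep post-miss samples in the primary model?** The computed shift is tiny, so that would also be defensible. Leaving them out keeps the plan's stated intent, and the sensitivity analysis shows whether the choice matters.

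**Conclusion.** The point holds as a matter of precision and should be fixed before the final analysis. Followed as written, section 15.1 can remove whole series because of one undocumented dose, including on average 1.5 of 4 weekly samples per affected participant that were drawn while fully dosed. Pooled power would fall from 81% to between about 80% (p = 0.1%) and 72% (p = 1%). That rests on assumed independent misses, no replacement of one-miss completers, and an SD and control number back-solved from section 15.4. The gap in the wording does not depend on these figures; its practical size does.

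A reader might go further and infer four things that the documents do not support:
- That the comparison with MSM controls is biased. None is shown, and the computed shift is negligible.
- That the study is underpowered. No miss rate is given, and replacement is available.
- That the dose count is in conflict. The 28 to 30 days in section 5.1 is described as study duration, and sections 9.6 and 14 give no scheduled number of doses.
- That replacement clashes with the limit of 48 in section 7.1. That limit sits beside an explicit replacement provision, and no conflict is demonstrated.

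**What to change.** 1. In section 15.1, define the PK set by sample, for example: *The primary model uses each dried blood spot collected before the participant's first undocumented dose (sections 9.4.3 and 9.6), including those from participants later excluded under section 9.6.*
2. Add a sensitivity analysis that also keeps samples drawn after a single missed dose.
3. State in section 15.4 that the power assumes 48 evaluable participants.

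The cost is a few sentences and one extra model run. No adherence threshold, dose or visit changes. The downside is that some participants contribute only early visits, so the number at each week differs and should be reported.

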### **15.2 Demographic and Baseline Characteristics**

The following demographic variables at screening will be summarized: race, ethnicity, age, gender identity, birth sex.

### **15.3 Analysis of Primary Endpoint**

We will compare levels of TFV-DP in dried blood spots and rates of adverse events between trans men and trans women and a group of MSM historical controls from the iPrEx OLE study. We will compare log transformed TFV-DP levels using a linear mixed effects model with factors for group (trans men v. trans women v. MSM) and times (1, 2, 3 and 4 weeks after initiation) and their interaction with an unstructured covariance across visits and test for differences at between groups at each time point. If values appear to violate the normal distribution, we will obtain p-values and confidence intervals using the bootstrap. All p-values will be two-sided with p-value < 0.05 considered statistically significant. Adverse events will be compared using the Fisher exact test.

Adverse event rates will be coded by body system and MedDra classification term. Adverse events will be tabulated and will include the number of patients for whom the event occurred, the rate of occurrence, and the severity and relationship to study drug.

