## PROTOCOL SYNOPSIS

TITLE	I-BrEATHe - Interactions BEtween Antiretrovirals And Transgender Hormones.
SPONSOR	[name] and [name]
FUNDING ORGANIZATION	University of California Office of the President via the California HIV/AIDS Research Program
NUMBER OF SITES	1
RATIONALE	
Drug concentrations after receipt of oral Truvada Pre Exposure Prophylaxis (or PrEP) appeared to be lower in transgender women compared to Men who Have Sex with Men (MSM) in the iPrEx study. Reasons for the lower drug concentrations may be behavioral or biomedical, or a combination of both. There are few to no studies which investigate the potential drug to drug interactions between the components of Truvada (emtricitabine or FTC and tenofovir disoproxil fumarate or TDF) and feminizing hormones. In addition, no PrEP studies have ever included transgender men; therefore no knowledge exists on the potential interactions between FTC/TDF and masculinizing hormones.
 
The pharmacokinetic study, using directly observed therapy (DOT), is designed to address the question whether feminizing or masculinizing hormones affect FTC/TDF levels in transgender women or transgender men respectively.

STUDY DESIGN	This is a pharmacokinetic study
PRIMARY OBJECTIVE	Assess pharmacokinetic drug-drug interactions between tenofovir disoproxil fumarate/emtricitabine (TDF/FTC) and cross-sex hormone therapy.
SECONDARY OBJECTIVES	Assess Adverse Events related to TDF/FTC in transgender men and women and compare to historical controls in non transgender MSM
NUMBER OF PARTICIPANTS	48 (24 transgender women and 24 transgender men)
PARTICIPANT SELECTION CRITERIA	
Inclusion Criteria:
 
All subjects:
 
 
• HIV antibody seronegative (negative HIV rapid test),
 
• 18 years or older,
 
• Has a smart phone with access to two-way video call capability,
 
• Willingness to be contacted for a short call every day for 4 weeks,
 

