STATISTICS Primary Analysis Plan	We will compare levels of Tenofovir DiPhosphate (TFV-DP), the phosphorylated active tenofovir molecule in dried blood spots and rates of adverse events between trans men and trans women and a group of MSM historical controls from the iPrEx OLE study. We will compare log transformed TFV-DP levels using a linear mixed effects model with factors for group (trans men v. trans women v. MSM) and times (1, 2, 3 and 4 weeks after initiation) and their interaction with an unstructured covariance across visits and test for differences at between groups at each time point. If values appear to violate the normal distribution, we will obtain p-values and confidence intervals using the bootstrap. All p-values will be two-sided with p-value < 0.05 considered statistically significant. Adverse events will be compared using the Fisher exact test.
Rationale for Number of Participants	A sample size of 48 (24 trans women and 24 trans men) allows detection of a difference of 0.52 log difference (1.68 fold difference) in TFV-DP from dried blood spots with 81% power on a two-sided 0.05 level test at any time point between our trans participants and MSM historical controls. A difference of 0.70 log (2.0 fold difference) can be detected between either group (trans men or women), and MSM historical controls with 80% power on a two-sided 0.05 level test.

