PrEP is the newest and most promising biomedical HIV prevention intervention yet developed and tested. The first clinical trial of PrEP ('iPrEx' or iniciativa Profilaxis Pre-Exposición) included MSM and transgender women who were at higher risk for HIV infection, and found that daily oral Truvada PrEP reduced the risk of HIV acquisition by 44% on an intention to treat basis [1]. However, a sub-analysis of the iPrEx data conducted by Deutsch *et al*, found zero effectiveness on an intention to treat basis among the small subgroup of transwomen in the study [2]. Further analyses revealed that the subgroup of trans women in iPrEx who were using hormones were less likely to have protective drug levels than those trans women not on hormones (OR 0.14,  $p < 0.001$ ). It is unclear if this difference is behavioral (less drug uptake) or biomedical (drug-drug interactions) in nature, or due to some combination of these factors, given the lack of pharmacokinetic (PK) studies testing for interactions between cross-sex hormone therapy (HT) and TDF/FTC, the active ingredients of Truvada. While there are studies of systemic drug-drug interactions between oral contraceptives and TDF, no such studies have been done with FTC, and no studies have been done with gender affirming HT, which differs from hormonal contraception in several respects. Drug-drug interactions with bioidentical 17-beta estradiol used for gender affirming hormone therapy among transgender women have not been studied.

The Interactions BETWEEN Antiretrovirals And Transgender Hormones, or I-BrEATHe study, described in this protocol is a sub study of the TRIUMPH study. I-BrEATHe will address one of the secondary aims of the TRIUMPH study which is to assess the pharmacokinetic drug-drug interactions between cross-sex HT and daily oral FTC/TDF.

Given that there are no PrEP studies to date that have specifically enrolled trans identified men, or have looked at the interactions between masculinizing HT and FTC/TDF, I-BrEATHe will enroll both transgender women and men. Transgender men report sexual rapports without condoms both vaginally and anally (range 26-60%), exhibit patterns of STIs transmission and unwanted pregnancies. Transgender men also report use of sex for gender affirmation. Small convenience samples show that HIV prevalence is between 2-5% [3, 4]. To date, there are no programs or PrEP recommendations specific for transgender men.

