## 2.2 Overview of Clinical Studies

There have been a large number of trials conducted with Truvada PrEP, including several demonstration projects. While there is no evidence to suggest that TDF/FTC interacts with commonly used feminizing or masculinizing hormone regimens, and evidence from studies of ARV interactions with hormonal contraceptives have been reassuring, no direct study of these interactions has been conducted to date.

Our team led the only trans-specific sub analysis to date of the iPrEx randomized controlled trial (RCT) data as well as the open label extension (OLE) study, which included periodic dried blood spot (DBS) drug level monitoring [2]. In iPrEx, gender identity data was not collected using current best practices (“two-step” method [5]), making the identification of transgender participants in this multinational, multicultural and multilingual trial difficult. As all iPrEx participants had been assigned male sex at birth, a transgender subgroup of 339/2499 participants (14% of overall sample) was constructed comprised of the 29 (1%) who identified as women, 296 (12%) who identified as “trans”, and 14 (1%) who reported use of feminizing hormones. None had undergone gender affirming genital surgery. Compared with MSM, transgender women more frequently reported transactional sex, receptive anal intercourse without a condom, or more than 5 partners in the past 3 months. Excluding those with a male identity who also used feminizing hormones, trans- and woman-identified participants were less likely to have TDF levels detected on random testing in the RCT (OR=0.39, 95% CI = 0.16 to 0.96, p=0.04). While there was no effectiveness of PrEP for transgender women on an intention-to-treat basis, none of the transgender participants who seroconverted had detectible drug levels at the time of HIV diagnosis. In comparison to MSM in the OLE, transgender participants had less time with protective drug concentrations (17% vs 35%, p<0.001) and were less likely to have concentrations indicating > 3 tablets/week (OR 0.71, 95% CI 0.49 to 1.03, p=0.07). Of the two transgender women who seroconverted during the OLE, both had drug levels below 350 fmol/punch in DBS, the level associated use of 2 tablets per week at the time of seroconversion. The lower concentrations were more likely if the transgender women used feminizing hormones.

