## 3 STUDY RATIONALE

The fact that concentrations of FTC/TDF were especially low among transgender women reporting use of feminizing hormones in the iPrEx study, which may reflect less PrEP use or a drug-drug interaction, is of high interest given that concerns about the impact of PrEP

on gender affirming hormone therapy is the main barrier for uptake of PrEP among transgender women [7]. While transgender men as a group have also been shown to be at elevated risk for HIV infection [4, 8], no information about PrEP use and drug levels is available for transgender men since they have never been formally included in PrEP research. Therefore, there are no data on the potential effects of testosterone on FTC/TDF drug concentrations. FTC/TDF drug concentrations have emerged as strong correlates of protection in PrEP trials, accounting for the majority of the variation in PrEP benefits across trials and across individual participants in trials. For example, while oral FTC/TDF PrEP had 44% efficacy on an intention to treat basis in iPrEx, the protective effect was more than 90% among those with detectable drug and negligible among those with no detectable drug in blood [1, 9].

The pharmacokinetic study of PrEP metabolites concentrations in association with feminizing and masculinizing hormones using directly observed therapy (DOT) will allow to establish whether interactions exist between these drugs. I-BrEATHe also provides an opportunity to include transgender men in PrEP research. Though transgender men are likely to be at lower risk for HIV acquisition than transgender women, the lack of available data regarding use of PrEP in transgender men must be remediated. I-BrEATHe will recruit equal numbers of transgender women who are using estradiol plus spironolactone (the most common HT regimen) and transgender men who are using testosterone. The primary aim will be to measure the intracellular active metabolites of TDF/FTC, tenofovir diphosphate (TFV-DP) and emtricitabine triphosphate (FTC-TP), levels in DBS collected after 1, 2, 3, and 4 weeks of video-observed Truvada for PrEP daily dosing, and comparing drug levels in the two groups receiving HT to previously acquired DBS drug levels data in MSM [9-11].

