### **15.4 Sample Size**

A sample size of 48 (24 trans women and 24 trans men) allows detection of a difference of 0.52 log difference (1.68 fold difference) in TFV-DP from dried blood spots with 81% power on a two-sided 0.05 level test at any time point between our trans participants and MSM historical controls. A difference of 0.70 log (2.0 fold difference) can be detected between either group (trans men or women) and MSM historical controls with 80% power on a two-sided 0.05 level test. This is sufficient to determine if the differences in drug

concentrations observed in iPrEx OLE between MSM and trans women were due to interactions with feminizing hormone drug-drug interactions.

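### With no dosing criterion for the iPrEx OLE controls, a null or higher result in the 15.3 MSM comparison could not exclude a hormone interaction, contrary to the last sentence of 15.4

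*Combined protocol and SAP*

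**What the plan says.** The question behind the study is set out in section 2. Trans women on hormones in iPrEx were less likely to have protective drug levels, and "It is unclear if this difference is behavioral (less drug uptake) or biomedical (drug-drug interactions) in nature". The synopsis states that the study, "using directly observed therapy (DOT), is designed to address the question whether feminizing or masculinizing hormones affect FTC/TDF levels" in trans women and trans men.

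On the trans side, adherence is controlled at three points. Section 5.1 sets daily dosing under DOT, section 9.6 excludes a participant who misses two or more doses, and section 15.1 admits to the PK analysis only those who received all doses. Section 6.1 adds that the PK analyses depend on adherence.

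On the control side, section 15.3 names only "trans men and trans women and a group of MSM historical controls from the iPrEx OLE study". The synopsis has the same comparison: "molecule in dried blood spots and rates of adverse events between trans men and trans women and a group of MSM historical controls", again from iPrEx OLE. The mixed model has group, week (1 to 4 after initiation) and their interaction. No adherence criterion, selection rule, matching or dosing covariate is given for the controls.

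Section 2.2 says of iPrEx OLE that, compared with MSM, "transgender participants had less time with protective drug concentrations (17% vs 35%, p<0.001"), and that transgender participants were "less likely to have concentrations indicating > 3 tablets/week". The protocol therefore reads DBS concentrations as a measure of tablets taken.

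Section 15.4 gives the detectable differences and concludes: "This is sufficient to determine if the differences in drug" concentrations between MSM and trans women in OLE were due to interactions with feminizing hormones. Section 15 promises a later SAP that may modify these methods.

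**The concern.** DOT is the device that is meant to separate the behavioral explanation from the biomedical one. As written, it removes the behavioral explanation from the trans groups only. The MSM are the only group in the model not enrolled for hormone use, and the primary objective (4.1) asks whether concentrations are lower than theirs. Hormone use is thus open to confounding with adherence.

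The likely direction works against the hypothesis. Lower control concentrations caused by missed doses would offset a real reduction in the trans groups. The practical risk is that a null result is reported as evidence of no interaction. A sample size deals with random error only; it cannot separate an interaction from a difference in dosing.

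**Working it through.** **Inputs.** From 15.4, two-sided 0.05 level: 0.52 log with 81% power (48 trans participants v. MSM) and 0.70 log with 80% power (24 v. MSM). The SD, the number of controls and the controls' adherence are not stated, so the power figures cannot be reproduced directly; they can be checked for consistency.

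**1. Scale.** exp(0.52) = 1.68 and exp(0.70) = 2.01. The logs are natural and the stated fold differences agree.

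**2. Implied standard errors.** SE = difference / (1.960 + z for the stated power).
- Pooled: 0.52 / (1.960 + 0.878) = 0.1832
- One group: 0.70 / (1.960 + 0.842) = 0.2499

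**3. Consistency.** With a common SD s and m controls, SE² = s²(1/n + 1/m). Subtracting the two gives s² = 48 × (0.2499² − 0.1832²) = 1.385, so s = 1.18. Then 1/m = 0.1832²/1.385 − 1/48 = 0.0034, so m is about 293. Rounding in the stated figures allows s from 1.11 to 1.23 and m from 138 to 1,727. The two statements are compatible with each other, but 15.4 does not fix the control number.

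**4. Effect of lower control exposure.** Let f be control exposure as a share of exposure under full daily dosing. It is assumed, and the SEs in step 2 are held fixed. The observed log difference shrinks from δ to δ + ln f, and the power to find trans levels lower is Φ((δ + ln f)/SE − 1.960).

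| f (assumed) | ln f | Pooled, δ = 0.52 | One group, δ = 0.70 |
|---|---|---|---|
| 1 | 0 | 81% | 80% |
| 0.9 | −0.105 | 62% | 66% |
| 0.8 | −0.223 | 37% | 48% |
| 5/7 | −0.336 | 17% | 31% |

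Example at f = 0.8, pooled: (0.52 − 0.223)/0.1832 − 1.960 = −0.34, and Φ(−0.34) = 37%.

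**5. Thresholds.** Power is 50% at f = exp(1.960 × SE − δ), which is 0.85 pooled and 0.81 for one group. The stated reduction is fully masked at f = exp(−δ), which is 0.59 and 0.50. With no hormone effect at all, the chance that trans levels appear significantly higher is Φ(−ln f/SE − 1.960). At f = 5/7 this is 45% pooled and 27% for one group.

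**6. Price of a smaller control set.** The one-group detectable fold difference at 80% power is exp(2.802 × s × √(1/24 + 1/m)). For s from 1.11 to 1.23 it is 3.00 to 3.38 with 12 controls, 2.45 to 2.70 with 24, and 2.18 to 2.37 with 48, against the stated 2.0. These control numbers are assumed, and s is the value implied for the present, unspecified control set.

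**The case against.** The strongest reply is that this is an omission and not a stated error. No section says that OLE dosing was unobserved or that the chosen controls are unrestricted; the phrase used is compatible with a selected subset, and the SAP is still to come. That is true, but section 15 does not require the SAP to restrict the controls, and 15.3 is the text in force.

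Four stronger readings are tempting and are not supported:
- *The comparison is uninterpretable whatever the result.* Under the bias argued here, a significantly lower trans level would be conservative evidence of a reduction, which is what objective 4.1 asks about.
- *The 35% in section 2.2 measures the shortfall.* It is time at protective concentrations in OLE and does not describe weeks 1 to 4 after initiation. No value of f can be derived from it.
- *Section 3 contradicts 15.3 on the control source.* Section 3 refers "to previously acquired DBS drug levels data in MSM [9-11"], and reference 10 is by its title a directly observed dosing study. However, section 10.3.1 attaches reference 9 to the iPrEx OLE procedures, and reference 11 is by title an assay paper. The text is ambiguous and needs clarifying; it does not prove a conflict.
- *Observed-dosing controls from those references must become the primary comparator.* Reference 10 enrolled healthy volunteers according to its title, whereas 4.1 calls for non-transgender MSM, and DBS processing here follows OLE procedures. A forced switch could exchange adherence confounding for population and assay confounding.

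It is also fair to say that DOT is not absolute: sections 9.4.3 and 10.4 accept an audio call, a self-filmed video or a text message as back-up. The stated restriction is nevertheless on one side only.

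**Conclusion.** The concern holds in a limited form. The documents hold the trans participants to full daily dosing and state no such restriction for the MSM controls, on an endpoint that the protocol itself says depends on adherence. If the controls took less than daily dosing, a null or higher result could not exclude a hormone interaction, and the last sentence of 15.4 is unsupported for those results. The stated power figures are not shown to be wrong; what fails is the causal conclusion drawn from them.

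The size of the bias is unknown. The power losses in the table show sensitivity only, and rest on an assumed f, a common SD and the SEs implied by 15.4. They do show that a modest shortfall would matter: control exposure of about 0.81 to 0.85 of full daily dosing is enough to bring power down to 50%. Because this bears on the primary objective, it should be settled before control data are analysed.

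**What to change.** In 15.3, or in the SAP before control data are analysed:
- Restrict the primary MSM comparison to controls with dosing comparable to the DOT participants and with samples at matched weeks since initiation. This may be an iPrEx OLE subset whose adherence is established independently of TFV-DP, since choosing controls by the outcome itself would bias the contrast. It may instead be observed-dosing controls, if population and DBS assay comparability are confirmed.
- Report any comparison with unrestricted OLE controls as descriptive. If no suitable controls exist, report the whole MSM comparison as descriptive.

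In section 3, say whether references 9 to 11 are the control source, and align this with the synopsis and 15.3.

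In 15.4, state the control number and SD, restate the detectable difference for the controls chosen, and delete the closing sentence or make it conditional on comparable dosing.

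The cost is wording, a data request, possibly an assay-comparability check and a new sample-size statement; participants' visits and procedures do not change. The downside is fewer controls and probably a less favourable detectable difference, as step 6 of the working illustrates. A smaller SD among controls with comparable dosing would offset part of this, but the documents give no SD. Nor do they say whether OLE holds an adherence measure independent of drug level.
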